### 6.2.2 Adverse Events

#### 6.2.2.1 Definitions of Adverse Events

The investigator is responsible for reporting all TEAEs that are observed or reported during the study, regardless of their relationship to study drug or their clinical significance.

An AE is defined as any untoward medical occurrence in a subject enrolled into this study regardless of its causal relationship to study drug. Subjects will be instructed to contact the investigator at any time if any symptoms develop.

A TEAE is defined as any event not present before exposure to study drug or any event already present that worsens in either intensity or frequency after exposure to study drug.

An SAE is defined as any event that:

- Results in death
- Is immediately life-threatening
- Requires inpatient hospitalization or prolongation of existing hospitalization
- Results in persistent or significant disability/incapacity, or
- Is a congenital anomaly/birth defect

Important medical events that may not result in death, be life-threatening, or require hospitalization may be considered SAEs when, based upon appropriate medical judgment, they may jeopardize the subject or may require medical or surgical intervention to prevent one of the outcomes listed in this definition. Examples of such medical events include allergic bronchospasm requiring intensive treatment in an emergency department or at home, blood dyscrasias or convulsions that do not result in inpatient hospitalization, or the development of drug dependency or drug abuse.

### **6.2.2.2 Eliciting and Documenting Adverse Events**

Adverse events will be collected and assessed from the time the subject signs the ICF until they exit from the study or 30 days after the last dose of the study drug, whichever is later. Any AE that occurs after the first dose of study drug is considered treatment-emergent.

Serious AEs that occur more than 30 days after exit from the study or 30 days after the last dose of study drug, whichever is later, will be reported to PPD/sponsor, only if the investigator considers them related to study drug.

At every study visit, subjects will be asked a standard nonleading question to elicit any medically related changes in their well-being. They will also be asked if they have been hospitalized, had any accidents, used any new medications, or changed concomitant medication regimens (both prescription and OTC medications).

In addition to subject observations, AEs will be documented from any data collected on the AE page of the eCRF (eg, laboratory test results or physical examination findings) or identified from review of other documents (eg, subject diaries) that are relevant to subject safety.

### **6.2.2.3 Reporting Adverse Events**

All AEs reported or observed after the subject signs the ICF will be recorded on the AE page of the eCRF. Information to be collected includes the following:

- Event term
- Time of onset
- Location of event (ocular or non-ocular); if location is an eye, the study or fellow eye must be identified)
- Investigator-specified assessment of severity
- Investigator-specified assessment of relationship to study drug, study procedure (procedure must be identified), or laboratory test result (laboratory test parameter must be identified)
- Date of resolution
- Seriousness
- Any required treatment or evaluations
- Any required changes in study drug administration (treatment interruption, dose change, treatment discontinuation, study withdrawal, or none)
- Outcome

Adverse events resulting from concurrent illnesses, reactions to concurrent illnesses, reactions to concurrent medications, or progression of disease states must also be reported. All AEs will be followed to adequate resolution. The Medical Dictionary for Regulatory Activities (MedDRA) will be used to code all AEs.

Any medical condition that is present at the time that the subject is screened but does not deteriorate should not be reported as an AE. However, if the medical condition deteriorates at any time during the study, it should be recorded as an AE.

Any AE that meets the SAE criteria (Section 6.2.2.1) must be reported to the PPD Pharmacovigilance Department immediately (ie, within 24 hours) after the time the site staff first learn about the event. The following contact information is to be used for SAE reporting:

**6.2.2.4 Assessment of Severity**

The intensity of an AE refers to the extent to which an AE affects the subject's daily activities. The intensity of the AE will be rated as mild, moderate, or severe using the following criteria:

Mild: These events require minimal or no treatment and do not interfere with the subject's daily activities

Moderate: An AE that is sufficiently discomforting to interfere with normal activities

Severe: These events interrupt a subject's usual daily activities and may require systemic drug therapy or other treatment. Severe events are usually incapacitating

When changes in the severity of an AE occur more frequently than once a day, the maximum intensity for the event should be noted for that day. Any change in intensity of signs and symptoms over a number of days will be captured by recording a new AE, with the amended intensity grade and the date (and time, if known) of the change. Changes in the intensity of an AE should be documented to allow an assessment of the duration of the event at each level of intensity to be performed.

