### **7.9.4.1 Adverse Events**

All AEs will be listed and all TEAEs will be summarized. Adverse events will be deemed treatment-emergent if the onset date is on or after the date of first treatment, Day 1. Events that are not treatment emergent will be listed separately and together with all other AEs. Ocular TEAEs will be summarized separately from non-ocular TEAEs. Ocular TEAEs will be summarized for the study eye, the fellow eye, and either/worse eye (eg, a subject will be counted if the given event occurred in either the study or fellow eye. When events are summarized by relationship or severity, the event with the greatest relationship or severity will be used).

Treatment-emergent AEs will be summarized by treatment group, presenting the number and percentage of subjects having a TEAE in each system organ class and having each individual TEAE based on the preferred term. Additionally, TEAEs will be summarized by the number of events per 100 person-years of follow-up. Treatment-emergent AEs will also be tabulated according to intensity and causality. Subjects who experienced multiple TEAEs for a preferred term (PT) will be counted once, similarly for subjects with multiple TEAEs per system organ class (SOC).

Deaths, SAEs, and TEAEs leading to discontinuation of study drug will be listed separately and, if appropriate, summarized by treatment group, SOC, and PT.

The incidence of AEs over time may also be summarized.

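### The date-only TEAE rule in section 7.9.4.1 takes in AEs that start on Day 1 before the first dose, and nothing supplied says that split AE records of one continuing event count once in the event rate

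*Combined protocol and SAP*

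**What the plan says.** The protocol describes treatment emergence in three places.

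- Section 6.2.2.1 gives this TEAE definition: "any event not present before exposure to study drug or any event already present that worsens in either intensity or frequency after exposure".
- Section 6.2.2.2 says: "Any AE that occurs after the first dose of study drug is considered treatment-emergent".
- Section 7.9.4.1, which governs the tables, says: "Adverse events will be deemed treatment-emergent if the onset date is on or after the date of first treatment, Day 1".

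Collection begins well before dosing: "Adverse events will be collected and assessed from the time the subject signs the ICF" (section 6.2.2.2).

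On recording, section 6.2.2.4 says: "Any change in intensity of signs and symptoms over a number of days will be captured by recording a new AE". The new record carries the new grade and the date of the change, with the time if it is known. The stated purpose is to allow an "assessment of the duration of the event at each level of intensity".

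On counting, section 7.9.4.1 says that "TEAEs will be summarized by the number of events per 100 person-years of follow-up". Its count-once rule works on subjects: "Subjects who experienced multiple TEAEs for a preferred term (PT) will be counted once", and likewise for system organ class. Section 7.9 leaves data conventions to a separate SAP, which is not among the documents supplied.

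**The concern.** Safety is part of the primary objective (section 2.1). Section 7.9.4 plans no safety tests, so the descriptive TEAE tables carry the safety conclusion. Two features could blur them.

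First, the analysis rule looks only at the calendar date, whereas both definitions in section 6.2.2 turn on exposure. Events that began before any study drug was taken could be tabulated as treatment-emergent. In arms of 5 and 15 subjects, a single misclassified subject is visible in a percentage.

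Second, records and events are different units. The site opens a new record at each multi-day change of intensity, up or down. The event rate needs a count of events, and no supplied text says how records roll up into events. If each record were counted, the rate would mix how many events occurred with how often their intensity changed.

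**Working it through.** **Step 1. The three TEAE rules side by side.**

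| Case | 6.2.2.1 | 6.2.2.2 | 7.9.4.1 |
|---|---|---|---|
| Starts on Day 1 after the first dose | TEAE | TEAE | TEAE |
| Starts on Day 1 before the first dose, does not worsen | Not a TEAE | Outside its rule | TEAE |
| Starts before Day 1, worsens after dosing | TEAE | Depends on whether the new record counts as an occurrence | TEAE only if the date of change is used as the onset date |
| Starts before Day 1, only improves after dosing | Not a TEAE | Arguably a TEAE, through the new record | TEAE only if the date of change is used as the onset date |

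The second row is a direct conflict. It needs no assumption about split records. The last two rows depend on a convention that the protocol does not state.

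**Step 2. Can the second row occur?** AEs are recorded from consent. A predose blood sample is taken on Day 1 (section 6.4, Table 13–2), and the first dose is given during that same visit (Table 13–1, footnote a). So there is a short interval on Day 1 in which an AE can begin before exposure. Section 6.2.2.3 lists the time of onset among the items collected.

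**Step 3. Effect on subject incidence.** Planned arm sizes are 15, 15 and 5 (section 3.1), which agree with 35 split 3:3:1 (35 × 3/7 = 15; 35 × 1/7 = 5). One subject whose only AE is a Day 1 pre-dose AE adds:

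- placebo: 1/5 = 20.0 percentage points
- dose arm: 1/15 = 6.7 percentage points

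With a date-and-time rule, that subject adds 0.

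**Step 4. Effect on the event rate.** The plan gives no figure to reproduce and does not define the follow-up time in the denominator. For illustration, assume the planned arm sizes and 112 days (12 + 4 weeks) for every subject.

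- Person-years = n × days / 365.25; rate = 100 × count / person-years.
- Placebo: 5 × 112/365.25 = 1.533 person-years. One record gives 100/1.533 = 65.2; three give 300/1.533 = 195.7.
- Dose arm: 15 × 112/365.25 = 4.600 person-years. One record gives 100/4.600 = 21.7; three give 300/4.600 = 65.2.

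An event that goes from mild to moderate and back to mild over several days makes three records under section 6.2.2.4. Counted by record it contributes 195.7 on placebo or 65.2 in a dose arm. Counted as one event it contributes 65.2 or 21.7.

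Other follow-up lengths change the contribution of one record as follows:

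| Days assumed | Placebo | Dose arm |
|---|---|---|
| 85 (Day 1 to Day 85) | 85.9 | 28.6 |
| 112 | 65.2 | 21.7 |
| 113 (to Day 113) | 64.6 | 21.5 |
| 115 (30 days after a last dose on Day 85) | 63.5 | 21.2 |

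**Step 5. What the threefold contrast means.** 65.2/21.7 is 3, which is simply 15/5. If events are split into k records on average in every arm, each arm's rate is multiplied by the same k and the ratio between arms is unchanged.

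**The case against.** The date rule errs towards inclusion. It can add a Day 1 pre-dose AE but cannot drop one that starts after dosing, and all AEs are listed, including those that are not treatment-emergent. The interval on Day 1 is short, with the first dose preferably given before noon. All of this stands and limits the size of the point. It does not remove the conflict, which lies within the protocol whatever the SAP says.

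On the event rate, rolling records up into events is the kind of convention that section 7.9 leaves to the SAP. Section 6.2.2.4 also speaks of one event with several levels of intensity, which leans against counting by record. This largely stands: the text permits double counting but does not prescribe it, and counting by record is probably not intended.

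Splitting also has a use. A record dated at a post-dose worsening is a natural way to capture a pre-existing AE that becomes a TEAE under section 6.2.2.1. That stands too, so linking must not lose such events. Finally, a clock time may be missing: section 6.2.2.4 asks for the time of a change only if known. A date-and-time rule therefore needs a default.

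A reader might infer that the safety tables will overstate TEAEs on placebo more than on MT-0814, given 65 against 22 per extra record. The documents do not support that. The contrast is arm size alone, and nothing suggests that splitting differs by arm. Nor does repeated recording of an event inflate subject-level incidence, because the count-once rule covers it.

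**Conclusion.** The point holds, as a minor one. The firm part is that section 7.9.4.1 counts an AE that starts on Day 1 before the first dose and does not worsen, contrary to sections 6.2.2.1 and 6.2.2.2. One subject with no other AE moves TEAE incidence by 20.0 points on placebo or 6.7 points in a dose arm, at the planned arm sizes with all subjects dosed.

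The softer part is that one continuing event can be counted more than once in the rate per 100 person-years, unless the SAP links the records. About 65 (placebo) or 22 (dose arm) per extra record illustrates arm size under an assumed 112 days for all; it does not estimate the error. The documents give no frequency of split records or of Day 1 pre-dose AEs, so the total effect cannot be estimated.

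A reader might also infer that pre-dose AEs that merely improve will be tabulated as TEAEs. That follows only if the date of change becomes the onset date, which the protocol does not say.

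**What to change.** **TEAE rule.** Use the section 6.2.2.1 definition in sections 6.2.2.2 and 7.9.4.1, applied with onset date and time relative to the first dose. If the onset time of a Day 1 AE is missing, treat the AE as treatment-emergent.

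**Event counts and rates.** In section 7.9.4.1 or the SAP, link consecutive intensity-change records of the same unresolved event and count that event once:

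- an event that starts after dosing takes its first onset and its maximum intensity;
- an event that starts before dosing counts only if it worsens after dosing, dated at the first post-dose worsening and with the maximum post-dose intensity;
- an event that starts before dosing and only improves is not a TEAE.

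Keep the split records for listings and for duration by intensity. If the SAP already holds a linking rule, a cross-reference in section 7.9.4.1 settles that part; the TEAE wording in the protocol still needs to be aligned.

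**Cost.** The change needs wording, a derived linking flag, and some masked review before database lock to separate continuing events from recurrences, because the items listed in section 6.2.2.3 do not include a link to an earlier record. It needs no new visits or assessments.

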**6.2.2.5 Assessment of Causality**

The investigator's assessment of an AE's relationship to study drug is part of the documentation process, but it is not a factor in determining what is or is not reported in the study. If there is any doubt as to whether a clinical observation is an AE, the event should be reported.

The relationship or association of the study drug in causing or contributing to the AE will be characterized using the following classification and criteria:

Related: A clinical event, including laboratory test abnormality, occurs in a plausible time relationship to treatment administration, and which concurrent disease or other drugs or

chemicals cannot explain. The response to withdrawal of the treatment (dechallenge\*) should be clinically plausible. The event must be definitive pharmacologically or phenomenologically, using a satisfactory rechallenge† procedure, if necessary.

\*Dechallenge is when a drug suspected of causing an AE is discontinued. If the symptoms of the AE disappear partially or completely, within a reasonable time from drug discontinuation, this is termed a positive dechallenge. If the symptoms continue despite withdrawal of the drug, this is termed a negative dechallenge. Note that there are exceptions when an AE does not disappear upon discontinuation of the drug, yet drug-relatedness clearly exists (for example, as in bone marrow suppression, fixed-drug eruptions, or tardive dyskinesia).

†Rechallenge is when a drug suspected of causing an AE in a specific subject in the past is re-administered to that subject. If the AE recurs upon exposure, this is termed a positive rechallenge. If the AE does not recur, this is termed a negative rechallenge.

Unrelated: A clinical event, including laboratory test abnormality, with little or no temporal relationship with treatment administration. May have negative dechallenge and rechallenge information. Typically explained by extraneous factors (eg, concomitant disease, environmental factors, or other drugs or chemicals).

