### 6.3 Pregnancy

Female subjects of childbearing potential (defined in Inclusion Criterion 10 of Section 4.1.1) and male subjects are required to use effective contraception throughout the study.

Acceptable methods of contraception for female subjects include oral contraceptives, other hormonal contraceptives (vaginal products, skin patches, or implanted/injectable products), or mechanical products such as an intrauterine device or barrier methods (diaphragm, condoms, spermicides). Note: Female subjects who are actively practicing abstinence or who have a partner that is sterile (eg, vasectomy) will be permitted to participate in the study without contraception use.

The acceptable method of contraception for male subjects is the use of a condom plus spermicide. Note: Male subjects who are actively practicing abstinence or who have a partner that is sterile (eg, postmenopausal or undergone successful sterilization [both defined in Inclusion Criterion 10 of Section 4.1.1]) will be permitted to participate in the study without contraception use.

Pregnancy is not regarded as an AE unless there is a suspicion that an investigational product may have interfered with the effectiveness of a contraceptive medication. Any pregnancy that occurs during study participation must be reported using a clinical study pregnancy form. To ensure subject safety, each pregnancy must be reported to PPD/sponsor within 2 weeks of learning of its occurrence. The pregnancy must be followed up to determine its outcome (including spontaneous miscarriage, elective termination, normal birth, or congenital abnormality) and the health status of mother and child, even if the subject was discontinued from the study. Pregnancy complications and elective terminations for medical reasons must be reported as an AE or SAE. Spontaneous miscarriages and congenital abnormalities of the child must be reported as an SAE.

Any SAE occurring in association with a pregnancy, brought to the investigator's attention after study completion, and considered by the investigator as possibly related to the study treatment, must be promptly reported to PPD/sponsor.

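### The two-level causality scale has no clear place for a plausibly timed event with a possible alternative cause, so the related-TEAE table is likely to be understated or unreliable

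*Combined protocol and SAP*

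**What the plan says.** Section 6.2.2.5 (Assessment of Causality) introduces the scale as describing study drug's part in causing or contributing to an AE. It then defines two levels.

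- *Related*: the event "occurs in a plausible time relationship to treatment administration", and it is one that concurrent disease or other drugs or "chemicals cannot explain". The response to stopping treatment should be clinically plausible. The last condition is "The event must be definitive pharmacologically or phenomenologically", with rechallenge if necessary.
- *Unrelated*: an event "with little or no temporal relationship with treatment administration". Dechallenge and rechallenge information may be negative, and extraneous factors such as other disease or other drugs typically explain the event.

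The rating is used in two places. Section 7.9.4.1 plans a table from it: "Treatment-emergent AEs will also be tabulated according to intensity and causality". Section 6.2.2.2 uses it as a reporting filter for SAEs arising after the 30-day limit, which are reported "only if the investigator considers them related to study drug". Section 6.3 uses another threshold for pregnancy-associated SAEs that come to light after study completion: those "considered by the investigator as possibly related to the study treatment".

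**The concern.** A two-level scale works only if every event falls into one level or the other. Here one definition is set close to certainty and the other close to absence of a temporal link. The common middle case, an event that study drug might have caused but something else might also explain, is left to each investigator.

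That middle case should be frequent in this trial. Subjects are 50 or older, concomitant medication is recorded throughout, and the causality definitions expressly cover laboratory abnormalities. Serum chemistry is drawn weekly through Week 12 (Table 13–1), a schedule that Amendment 3 expanded after a safety review committee discussion.

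Safety and tolerability head the primary objective in 2.1, and 1.3 describes the human safety profile as limited. The placebo arm has 5 subjects and safety is summarised without testing (7.9.4), so the comparison with placebo is weak. If an event had an assumed background rate of 20%, the chance of seeing none in 5 placebo subjects would be 0.8^5 = 0.33. Readers will therefore lean on investigator causality more than they would in a larger trial.

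**Working it through.** The plan states no figure that depends on this scale, so there is nothing to reproduce. The check is one of logic.

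**Step 1. Test case.** Take a hypothetical rise in ALT at Week 3 in a subject who also takes another medicine that could raise ALT. No rechallenge is done.

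| Condition in 6.2.2.5 | Force of the wording | Test case |
|---|---|---|
| *Related*: plausible timing | firm | met |
| *Related*: other causes cannot explain it | firm | not met, or doubtful |
| *Related*: plausible response to withdrawal | expectation, with exceptions in the footnote | unknown |
| *Related*: definitive event | firm (must) | not met |
| *Unrelated*: little or no temporal link | leading criterion | not met |
| *Unrelated*: explained by extraneous factors | descriptive (typically) | possibly met |

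The event fails at least one firm condition of *Related* and the leading criterion of *Unrelated*. Only the soft descriptor under *Unrelated* leans towards it.

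**Step 2. Internal consistency.** The lead-in asks about causing or contributing. An event to which the drug contributed alongside another cause is one that the other cause can partly explain. The *Related* definition shuts out the contributory case that the lead-in sets out to capture.

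**Step 3. Is the gap filled elsewhere?**
- The sentence in 6.2.2.5 about doubt concerns whether an observation is an AE, not how to rate it.
- Section 6.2.2.3 collects the relationship to study drug but does not define it.
- Section 6.3 relies on a possibly-related level that the scale does not contain.
- Section 7.9.4.1 tabulates by causality with no rule for doubtful events.

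**Step 4. What depends on the rating.**
- Affected: the causality table in 7.9.4.1 and the late-SAE rule in 6.2.2.2.
- Not affected: recording of AEs (6.2.2.1, 6.2.2.3), TEAE incidence by arm, SOC and PT (7.9.4.1), and the 24-hour reporting of SAEs in the collection window (6.2.2.3).

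**Step 5. Illustration under assumed rates.** The documents give none of these rates. Let n = 15 subjects in one active arm (3.1). Let p be the share with at least one TEAE that has a reasonable possibility of relation to study drug, and c the share of those subjects who would still be counted under the strict *Related* text.

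- Expected subjects with a related TEAE: n·p under a reasonable-possibility rule, n·p·c under the strict reading.
- Chance of at least one such subject in the arm: 1 − (1 − p)^15 and 1 − (1 − p·c)^15.

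| p | Expected, reasonable possibility | Expected, c = 0.25 / 0.50 | Chance of ≥1, reasonable possibility | Chance of ≥1, c = 0.25 / 0.50 |
|---|---|---|---|---|
| 0.10 | 1.5 | 0.38 / 0.75 | 79.4% | 31.6% / 53.7% |
| 0.20 | 3.0 | 0.75 / 1.5 | 96.5% | 53.7% / 79.4% |
| 0.40 | 6.0 | 1.5 / 3.0 | about 100% | 79.4% / 96.5% |

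For p = 0.20 and c = 0.25: 1 − 0.80^15 = 0.965 and 1 − 0.95^15 = 0.537. With c = 1, where sites resolve every doubtful event as *Related*, nothing is lost. The table shows only that a strict reading could matter in an arm of this size. It does not estimate the effect.

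**The case against.** The strongest reply is that the direction of error is not fixed. An investigator who reads the opening of *Unrelated* literally would not use it for a plausibly timed event and might choose *Related*. The causing-or-contributing lead-in points the same way. A reader might infer that related-TEAE rates are bound to be understated, but the text does not support that certainty. What stands is that the same event could be rated in opposite ways across about 15 sites, with the mandatory wording of *Related* and the extraneous-factors sentence pulling towards *Unrelated*.

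A reader might also infer that *Related* requires a positive dechallenge and a rechallenge. It does not. Dechallenge is an expectation, the footnote concedes that relatedness can be clear without it, and rechallenge applies only if necessary. The firm conditions are timing, absence of another explanation, and the definitive event. Those three are enough to create the gap.

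Nor does the text leave the test case wholly unclassifiable, because the extraneous-factors sentence describes it fairly well. But using that sentence means setting aside the criterion placed before it.

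A broader inference, that safety reporting as a whole is compromised, fails too. Section 6.2.2.5 says that the rating does not decide what is reported, and 7.9.4.1 lists deaths, SAEs and TEAEs leading to discontinuation of study drug whatever their cause. Section 6.3 is only modest support: its threshold governs a narrow case in subjects aged 50 or older and feeds no table. It still shows two thresholds in one protocol for SAEs learned of late.

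**Conclusion.** The concern holds as a defect in definition with limited reach. Section 6.2.2.5 does not classify doubtful events cleanly and contradicts its own lead-in, and nothing else in the document repairs it. The related-TEAE table is likely to be understated or to vary by site, and a late SAE that is suspected but not definitive may go unreported.

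*Likely* rests on two assumptions: that a material share of plausibly timed events will have some alternative explanation, and that many investigators will give weight to the mandatory wording of *Related*. The documents support neither with a figure, so the size is unknown. Because the randomised comparison of all TEAEs does not depend on the scale, this should be corrected but does not undermine the safety evaluation as a whole.

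**What to change.** Replace the two definitions in 6.2.2.5 with an exhaustive pair:

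- *Related*: there is a reasonable possibility that study drug caused or contributed to the event. An alternative cause does not by itself exclude this.
- *Unrelated*: there is no reasonable possibility that it did.

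Keep dechallenge and rechallenge as supporting evidence. Use the same threshold for late SAEs in 6.2.2.2, for pregnancy-associated SAEs in 6.3 and for the tabulation in 7.9.4.1.

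The change needs protocol wording and eCRF completion guidance, with no added visits, subjects or procedures. It has two costs. More events will be labelled related, so that table will look less favourable. The protocol is also already at Version 4.0, so any events rated under the present wording would have to be re-rated, or flagged in the table, to avoid mixing two thresholds in about 35 subjects.
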